6.4.3 Ordering in tables, listings and figures

If the treatments are presented as columns, tables will be sorted by analysis visit and time point. Otherwise, tables will be sorted first by treatment, then by analysis visit and time point. The active treatments will be shown first in ascending dose order, and then placebo: CHF10067 1000 mg, CHF10067 2000 mg, CHF10067 3000 mg, CHF10067 Total and then placebo.

All tables and figures will be presented per treatment, unless specified otherwise.

All listings will be ordered by subject and then by analysis visit and time point (chronologically), unless specified otherwise.

In tables and figures showing several parameters, each parameter will begin on a new page and parameters will be sorted alphabetically, within the parameter category if applicable.

6.4.4 Raw SAS output

In addition to the statistical output as described in section 9, raw SAS output will be delivered in separate files as ‘Appendix to Table 14.x.x.x’ for all tables presenting inferential statistics. The layout of the appendices will be similar to the table (study identifier, SAS program name, production date, page count); presenting the raw SAS output in the body section.

6.4.5 eCTD tables

Additional tables will be delivered in separate files as ‘Appendix to Table 14.x.x.x’ for all tables presenting PK parameters: they will be created separately for each

Statistical Analysis Plan

CLI-10067AA1-01

Final Analysis

Final 1.0 of 30MAY2024

analyte and will present the subjects/profiles (if any), per treatment, showing $AUC_{0-t}/AUC_{0-\infty} < 0.8$, C_{max} as the first point and pre-dose sample $> 5\% C_{max}$ per treatment.

7. CHANGES TO THE PLANNED ANALYSIS

7.1 CHANGES NOT COVERED BY PROTOCOL AMENDMENTS BEFORE UNBLINDING

- **“Immunogenicity Analysis”:** Section 2.2 of the SAP to clarify section ‘12.3.5.3 Immunogenicity’ of the study protocol.
Section 2.2 of this SAP, compared to Section 12.3.5.3 of the study protocol, provides clear definitions and a corresponding summary table on the whole Safety Set for: ADA evaluable subject, ADA positive subjects, ADA prevalence, ADA incidence (i.e., treatment-induced and treatment-boosted ADA) and nAb positive subject. As a consequence of the above update, the two summary tables on the subset of ADA positive subjects, initially foreseen in Section 12.3.5.3 of the study protocol, have been translated into a listing (see Listing 16.2.6.1 at Section 9.2 of the present document).
- **“Vital signs”:** Section 3.3 of the SAP to clarify section ‘12.3.5.4.3 Oxygen saturation’ of the study protocol.
While per protocol, individual time profile plots are not requested for oxygen saturation, these will be produced to be in line with the vital signs analysis.
- **“Lung function”:** Section 3.5 of the SAP to clarify section ‘12.3.5.4 Pulmonary assessments’ of the study protocol.
The following summary analysis is described in the protocol:

“The frequency of subjects with FEV1% and FVC% below the lower limit of normal at each timepoint will be listed and summarised with descriptive statistics.”

Since no normal ranges are available for the aforementioned parameters, this summary will not be produced.

- **“Placebo-corrected change from baseline”:** Section 3.4 of SAP to clarify Section ‘12.3.5.5 ECG’ of the study protocol.
Placebo-corrected change from baseline is erroneously mentioned in the protocol but it is not applicable for this study design. Therefore, none of the analyses related to placebo-related change from baseline will be produced.

	Statistical Analysis Plan	
CLI-10067AA1-01	Final Analysis	Final 1.0 of 30MAY2024

- **Section “12.3.6.1 TG2 in plasma” of the study protocol.**

The below text was erroneously included in the study protocol.
Therefore, the related analyses will not be produced.

“The TG2 levels in plasma obtained from healthy subjects will be summarised using descriptive statistics.

Box-plots summarising the pre-dose levels for treated subjects in the study, the healthy subjects’ external group, and each post-dose levels for the different doses for treated subjects will be presented.”

- **“By dose level”: SAP to clarify Section 12 of the study protocol.**

While across the study protocol ‘dose level’ could be equivalent to ‘cohort’, and across section 12 of the protocol analyses are defined to be performed by ‘dose level’, in the SAP all analyses have been defined as ‘by treatment’, separating the subjects receiving active study treatment and placebo as defined in section 6.4.2 of this SAP.

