7.2.7 Pulmonary assessments for safety evaluation

7.2.7.1 Spirometry

Spirometry will be assessed at the following timepoints: screening, 7, 28, 56, and 84 days post-dose and in case of early termination visit.

Spirometry will be assessed centrally. The specific procedures for centralized spirometry will be provided to the Investigator by the centralized spirometry company. The same brand and model of spirometer will be provided by the centralised spirometry company for all measurements and adjusted for the ATS/ERS standards [20]. Lung function measurements will be done with subjects sitting with the nose clipped after at least 10 minutes rest. Values will be corrected for body temperature and pressure (saturated) conditions.

The following parameters (but not limited to) will be recorded: FEV₁, FVC, FEV₁% of predicted normal and lower limit of normal value, FVC % of predicted normal and lower limit of normal value, and FEV₁/FVC ratio.

Predicted values of FEV₁ will be calculated according to formulas reported by Quanjer et al. [21].

For FEV₁ and FVC, the highest value from 3 technically satisfactory attempts will be recorded in the eCRF (irrespective of the curve they come from). The chosen value should not exceed the next one by more than 150 mL. If the difference is larger, up to 8 measurements will be made and the largest value be reported. In order to be considered as technically satisfactory attempts, measurements should be free from cough and false-start and meet all the ERS/ATS criteria. The FEV₁/FVC should be taken from the highest FEV₁ and FVC values (even if not coming from the same curve). The acceptability criteria for spirometry assessment will be further specified in separate documents.

For inclusion criterion no. 8 if the criterion is not met at screening, the subject may repeat the tests. If at that time the values fall within the ranges specified, the subject can be included in the study, otherwise the subject will be discharged and recorded as screening failure.

Clinical Study Code No.: CLI-10067AA1-01	Version No.: 6.0
EUDRACT No.: 2022-001079-15	Date: 06 July 2023

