9. SAFETY ASSESSMENTS

9.1 Safety Variables

Safety and tolerability will be assessed through the monitoring of the following:

- AEs and adverse drug reactions (ADRs)
- Vital signs (systolic and diastolic blood pressure, pulse rate, respiratory rate, and body temperature)
- Oxygen saturation measured via pulse oximetry
- 12-lead ECGs (heart rate, PR, QRS, and QTcF)
- Clinical laboratory evaluations: clinical chemistry (including fasting glucose) and haematology
- Physical examinations
- Spirometry (FEV₁, FVC, FEV₁ % of predicted normal and lower limit of normal value, FVC % of predicted normal and lower limit of normal value, and FEV₁/FVC ratio)
- Diffusing capacity (D_{LCO} [unadjusted], D_{LCO} % predicted, D_{LCO} corrected for haemoglobin, D_{LCO} corrected for haemoglobin % predicted, KCO, and VA)
- ADAs and nAb
- Analysis of systemic markers* of immediate hypersensitivity reactions pre-dose and post-dose (post-dose only if required) including:
 - markers of cytokine release syndrome (IFN- γ , TNF- α , IL-1 β , IL-2, IL-4, IL-6, IL-8, IL-10, IL-12 (p70), and IL-13)
 - mast cell tryptase
 - complement markers (C3a, C5a, CH50, and SC5b-9)
 - CHF10067 IgE.

*During the study, the markers analysed may be adjusted as required. Any adjustment will be with consideration for subject safety and operational activities.

Clinical Study Code No.: CLI-10067AA1-01	Version No.: 6.0
EUDRACT No.: 2022-001079-15	Date: 06 July 2023

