12.3.5.4 Pulmonary assessments

12.3.5.4.1 Spirometry

The FEV₁, FVC, FEV₁/FVC, FEV₁% of predicted and FVC% of predicted, will be summarised by dose level as absolute value, and absolute and relative change from baseline (i.e., the assessment at screening between Days -28 to -3) at each post-dose timepoint using descriptive statistics and 95% CIs. The frequency of subjects with FEV₁% and FVC% below the lower limit of normal at each timepoint will be listed and summarised with descriptive statistics.

Time profile plots by dose level will be presented for mean absolute and relative changes from baseline.

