3.5 LUNG FUNCTION

3.5.1 *Available data*

The following lung function parameters are collected:

	Statistical Analysis Plan	
CLI-10067AA1-01	Final Analysis	Final 1.0 of 30MAY2024

- Spirometry: Forced Expiratory volume in 1 second (FEV₁), predicted FEV₁, percent predicted FEV₁, forced vital capacity (FVC), predicted FVC, percent predicted FVC and FEV₁/FVC ratio.
Spirometry will be assessed at the following timepoints: screening, 7, 28, 56, and 84 days post-dose and in case of early termination visit.
- Diffusing capacity: D_{LCO} [unadjusted], D_{LCO} % predicted, D_{LCO} corrected for haemoglobin, D_{LCO} corrected for haemoglobin % predicted, carbon monoxide transfer coefficient [KCO], and alveolar volume [VA].
Diffusing capacity will be assessed at the following timepoints: screening, 28, 56, and 84 days post-dose and in case of early termination visit.

3.5.2 *Presentation of results*

Spirometry:

Spirometry parameters will be summarised by means of descriptive statistics (with their 95% CI) at each analysis time point by treatment. Actual values, changes from baseline and relative changes from baseline will be tabulated.

Graphs of the absolute and relative mean changes from baseline over time will be prepared by treatment.

All spirometry parameters will be listed.

Diffusing capacity:

Diffusing capacity parameters will be summarised by means of descriptive statistics (with their 95% CI) at each analysis time point by treatment. Actual values, changes from baseline and relative changes from baseline will be tabulated.

Graphs of the absolute mean changes from baseline over time will be prepared by treatment for D_{LCO} % predicted and D_{LCO} corrected for haemoglobin.

All diffusing capacity parameters will be listed.

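### SAP 7.1 cancels the protocol's only spirometry count of subjects for want of normal ranges, although the protocol requires the lower limit of normal to be recorded; nothing replaces the count

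*SAP*

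**What the plan says.** **Protocol.** The spirometry procedure (7.2.7.1) includes "FVC % of predicted normal and lower limit of normal value" in the parameters to be recorded, and the safety variables in 9.1 include "FEV₁ % of predicted normal and lower limit of normal value". The LLN also appears in the protocol outline and in the procedures for screening (7.1.1), the treatment period (7.1.2) and early termination (7.1.3). One vendor supplies a single spirometer model to all sites: "Spirometry will be assessed centrally". Section 12.3.5.4.1 then plans that the frequency of subjects with FEV1% and FVC% "below the lower limit of normal at each timepoint will be listed and summarised with descriptive statistics". This is the only categorical summary under pulmonary assessments; diffusing capacity and oxygen saturation have continuous summaries only.

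**SAP.** Section 3.5.1 lists predicted and percent predicted values ("percent predicted FEV₁, forced vital capacity (FVC), predicted FVC, percent predicted FVC and FEV₁/FVC ratio") but no LLN. Section 7.1 withdraws the count: "Since no normal ranges are available for the aforementioned parameters, this summary will not be produced". For spirometry, 3.5.2 keeps descriptive statistics with 95% CIs, a listing and mean plots: "Graphs of the absolute and relative mean changes from baseline over time will be prepared by treatment". Section 9 contains no threshold count and no individual plot for spirometry.

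**The concern.** The reason given for the deletion conflicts with the protocol's own data list. SAP 7.1 presents the item as a clarification, but it removes an analysis. Elsewhere in 7.1, for the placebo-corrected ECG change and the healthy-subject TG2 comparison, the SAP says the protocol text was a mistake. It does not say so here; availability is the only ground. The SAP states that it follows the latest protocol, and version 6.0 still requires both the LLN and the count. Either the SAP is wrong about availability, or safety data required by the protocol were not obtained and no explanation is given.

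At stake is how a safety trial in a disease that the protocol introduces as progressive loss of lung function will describe lung function. The SAP counts subjects for blood pressure (3.3) and QTcF (3.4) and gives shift tables for laboratory data (3.2.3). It plans individual plots for vital signs, oxygen saturation and ECG. Spirometry has neither a count nor an individual plot, so a reader must build from the listing how many subjects per dose were affected and whether the same ones were affected at successive visits.

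**Working it through.** **1. Group sizes.** Protocol 12.1 gives 6 active and 2 placebo subjects in each of 3 cohorts: 3 × (6 + 2) = 24, matching the stated total. Active subjects: 3 × 6 = 18. Pooled placebo (SAP 6.4.2): 3 × 2 = 6. The protocol has no power calculation, so there is no planned effect size to reproduce.

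**2. What the mean and CI show.** Suppose one of six subjects falls by x and five do not change.

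- Mean = -x/6.
- Sum of squared deviations = 5x²/6, so the variance is x²/6, SD = x/√6 and SE = x/6.
- Hence t = (-x/6)/(x/6) = -1 whatever the size of x. The 95% t interval (5 degrees of freedom, SAP 6.4.1) therefore always includes 0.

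| Fall x | Mean | 95% CI | Median | Minimum | Mean in CHF10067 Total (n = 18) |
|---|---|---|---|---|---|
| 10 | -1.67 | -5.95 to 2.62 | 0 | -10 | -0.56 |
| 15 | -2.50 | -8.93 to 3.93 | 0 | -15 | -0.83 |
| 20 | -3.33 | -11.90 to 5.24 | 0 | -20 | -1.11 |
| 30 | -5.00 | -17.85 to 7.85 | 0 | -30 | -1.67 |

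A simulation added normal between-subject variation to falls of 10 and 20 points, with an assumed SD of 3, 5 or 8 points. The interval lay wholly below 0 in 0.1% to 4.3% of cohorts.

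**3. What the retained outputs show.** SAP 6.4.1 also requires the median, minimum and maximum, and Tables 14.3.5.1 and 14.3.5.2 apply these to absolute and relative change by treatment and time point. The minimum column above shows the fall in full, and Listing 16.2.11.1 gives every subject's changes. But a minimum does not count. If one subject falls by 15 or two do, the minimum is -15 and the median is 0 in both cases; the mean moves from -15/6 = -2.5 to -30/6 = -5.0. A minimum of -15 at Days 28, 56 and 84 may be one subject three times or three subjects once each.

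**4. What the cancelled count would have shown.** It measures status. A relative fall of 10% takes a subject newly below the limit L only if the baseline lies between L and L/0.9. The documents give no LLN values, so L is assumed, in % predicted:

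- L = 75: baselines 75 to 83.3
- L = 80: baselines 80 to 88.9
- L = 85: baselines 85 to 94.4

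Entry allows FVC from 50% predicted (Protocol 4.2). If baselines were uniform over 50 to 100 (an assumption), (L - 50)/50 = 50%, 60% or 70% would start below the limit. Only 8.3/50, 8.9/50 or 9.4/50, about 17% to 19%, would be newly flagged by such a fall.

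**The case against.** A reader might infer that one subject's fall disappears from the report. The documents do not support that: the minimum change is tabulated, Table 14.3.5.2 is marked as a key first result, and every subject is listed. Subjects are also counted by another route. Protocol 7.1.2 and 10.8 require clinically significant changes to be reported as adverse events, and SAP 3.1.3 tabulates subjects with such events. That count depends on the investigator's judgement and is not based on the spirometry values.

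A reader might also infer that the LLN values were in hand and were ignored. The documents do not show this. The SAP (30 May 2024) postdates protocol version 6.0 (6 July 2023) and may be reporting what was delivered. Nor is the change concealed; it is disclosed in 7.1 with a reason.

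Finally, the cancelled table is a weak detector of decline: a subject already below the limit who falls further stays in the same cell. This stands, and it means that restoring the table alone would close only part of the gap. It does not justify removing a safety summary on a ground that the protocol contradicts.

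**Conclusion.** The point holds as a conflict between the documents and a gap in summarisation. A safety count specified in the protocol is cancelled on a ground at odds with the protocol's data list, the omission from SAP 3.5.1 is unexplained, and no other spirometry count or individual plot is planned. The consequence is moderate. Individual falls remain visible as minima and in the listing, but the number of subjects affected per dose and their course over visits are not summarised, and the mean of six carries only one sixth of a single fall. The dilution follows from the group size alone. The figures on newly flagged subjects rest on assumed limits and an assumed uniform baseline, and the simulation rests on assumed SDs. Whether LLN values exist in the trial data cannot be settled from the documents. This should be corrected.

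**What to change.** 1. Reconcile Protocol 7.2.7.1 and 9.1 with SAP 3.5.1 and 7.1. Obtain the LLN for FEV1 and FVC from the central spirometry vendor, or derive it from the reference equations used for the predicted values. The derivation assumes that those equations supply an LLN; Protocol 7.2.7.1 names equations for FEV1 only, so the source for FVC must be stated. Age, sex, race and height are collected at screening.
2. Add the LLN to SAP 3.5.1 and restore the count below it by treatment and visit, cross-tabulated against baseline status. If the LLN cannot be obtained, replace the sentence in 7.1 with the reason why data required by the protocol are absent.
3. Add individual plots of spirometry change by treatment, as SAP 7.1 already does for oxygen saturation.
4. Add a count of subjects by prespecified categories of the relative change in FVC, which the SAP already derives (6.2.2, Table 14.3.5.2). The sponsor should fix the cut points before unblinding.

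The cost is a transfer field or a short derivation, one or two tables and a figure, with no new measurement. The LLN table will add little for subjects who start below the limit; items 3 and 4 cover them.

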12.3.5.5 ECG

At each post-dose timepoint, the following statistics will be presented by dose level for 12-lead ECG parameters (heart rate, PR, QRS, QTcF):

- mean absolute value with its 95% CI
- mean change from baseline (i.e., the pre-dose assessment on Day 1) with its 90% CI
- mean placebo-corrected change from baseline with its 90% CI.

Time profile plots, individual and by dose level, will be presented for change from baseline (i.e., the pre-dose assessment on Day 1). Time profile plots of mean difference versus placebo in change from baseline will be presented by dose level for heart rate and QTcF.

The number and percentage of subjects with the following will be presented by dose level at each post-dose timepoint and at any post-dose timepoint:

- Males: QTcF > 450 ms, > 480 ms, and > 500 ms
- Females: QTcF > 470 ms and > 500 ms
- Both sexes: change from baseline in QTcF > 30 ms and > 60 ms.

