1.4 RANDOMISATION AND BLINDING

An interactive responsive technology (IRT) system will be used for randomisation and assignment to blind treatment (CHF10067 or placebo).

The Investigator, or designee, at the sites will use the IRT system to screen and randomise subjects and to assign treatment kits according to the randomisation list. Subjects will be randomised in a 3:1 ratio within each cohort to receive either CHF10067 or placebo. Randomisation will require a minimum of 2 subjects within each cohort not receiving antifibrotic treatment (including subjects with previous use of antifibrotic treatment that has been stopped for at least 2 weeks prior to screening). In each cohort, at least 24 hours must elapse between dosing of the first 2 subjects (1 CHF10067; 1 placebo) and the remaining 6 subjects. The IRT system will be used to coordinate the scheduling of Day 1 visits to be sure that this procedure is followed.

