3.4 ELECTROCARDIOGRAMS

3.4.1 *Available data*

The following electrocardiogram (ECG) parameters will be collected:

- Triplicate local 12-lead ECG at Screening: heart rate (HR), PR interval, QRS interval, QT interval, corrected QT interval (Fridericia) (QTcF) and the corresponding interpretation
- Local 12-lead single ECG at other visits: heart rate (HR), PR interval, QRS interval, QT interval, corrected QT interval (Fridericia) (QTcF) and the corresponding interpretation

ECGs will be performed at Screening visit, at pre-dose on Day 1, and Days 2, 7, 28, and 84 days post-dose and in case of early termination visit.

3.4.2 *Derivation rules*

Mean values of the triplicates will be calculated at Screening and rounded as detailed in section 6.3.4. Records belonging to the same triplicate will be identified using variable EGREFID. All records of the triplicate will be used to calculate the mean, even if less or more than the expected three. Throughout the analysis, including the derivation of baseline and abnormalities, the mean values will be used. Individual triplicate values will only be listed.

For QTcF interval (ms), the following abnormality categories are defined:

- Actual values:
 - Males:
 - > 450 ms
 - > 480 ms
 - > 500 ms
 - Females:
 - > 470 ms
 - > 500 ms
- Changes from baseline:
 - Increase from baseline >30 ms
 - Increase from baseline >60 ms

Note: The worst-case, as defined in section 6.2.5, is the highest value and associated change.

3.4.3 *Presentation of results*

Local safety 12-lead ECG parameters (HR, PR, QRS and QTcF) will be summarised by means of descriptive statistics at each analysis time point by treatment. Actual values (with their 95% CI) and changes from baseline (with their 90% CI) will be tabulated.

For QTcF, the number and percentage of subjects with abnormal actual values will be presented at each post-dose time point and at the worst-case post-baseline analysis visit by treatment.

For QTcF, the number and percentage of subjects with abnormal changes from baseline will be presented at each post-dose time point and at the worst-case analysis visit by treatment.

All ECG data will be listed.

Graphs of the mean changes from baseline over time will be prepared for the continuous ECG parameters by treatment. In addition, individual graphs of the changes from baseline over time will be presented by treatment.

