6.4 PRESENTATION OF RESULTS

6.4.1 *Calculation of descriptive statistics and percentages*

For continuous parameters, full descriptive statistics will only be presented if there are at least 2 non-missing observations. Alternatively, only the number of non-missing data points and mean are shown.

Descriptive statistics of non-PK data will include the number of non-missing data points, the arithmetic mean, the standard deviation (SD), the median, minimum and maximum.

Descriptive statistics of safety parameters will additionally include 95% (or 90%) confidence interval (CI) on the mean (based on t-distribution, without continuity correction).

Mean, median, SD and CI will be presented with one more decimal place than the individual values, with a maximum of 4 decimal places. Minimum and maximum will be presented with the same number of decimal places as the individual values, with a maximum of 3 decimal places.

Descriptive statistics of PK concentrations will include the number of non-missing data points, the arithmetic mean, SD, the median, minimum and maximum and the coefficient of variation (CV) % of arithmetic mean. If more than half of values are BLQ at a specific timepoint, then SD and CV% will not be calculated and reported as “NC” (not calculated) in the tables.

Descriptive statistics on PK parameters will additionally include geometric mean and geometric CV%, except t_{max} for which the descriptive statistics will include the number of non-missing data points, the median, minimum and maximum.

The descriptive statistics on PK data will be presented as described in section 6.3.4.

The slopes and their 90%CI from the power model on PK parameters will be presented with two decimals.

For event-type data, the denominator will be all subjects in the analysis set and phase. All treatments will be shown, even if no events are present.

For frequency tabulations and cross-tabulations, missing values will not be included in the denominator count when computing percentages. For cross-tabulations of post-baseline results versus baseline results, a ‘missing’ category will be shown for baseline results if applicable.

Percentages will be shown with one decimal place.

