6.4.2 Presentation of treatments

The following treatment labels will be used in the tables, listings and figures:

- CHF10067 1000 mg
- CHF10067 2000 mg
- CHF10067 3000 mg
- CHF10067 Total ⁺
- Placebo ^{*}
- Overall [#]

⁺ “CHF10067 Total” is the combination of “CHF10067 1000mg”, “CHF10067 2000mg” and “CHF10067 3000mg” treatment groups, will be shown for all demographics and safety tables (with the exception of disposition, analysis set, protocol deviations and PK).

^{*} All placebo subjects (from all cohorts) will be pooled into one “Placebo” group for presentation in tables and figures.

[#] Unless specified otherwise, an “Overall” column, to summarise all subjects over treatments (including placebo), will be presented only in tables showing data that are not affected by the study treatment (i.e., general characteristics analyses). The overall column will be shown last.

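### SAP 7.1 drops the protocol's only drug-minus-placebo contrast (ECG) as not applicable to the design, but the design supports it

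*SAP*

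**What the plan says.** Protocol 12.3.5.5 lists, for heart rate, PR, QRS and QTcF at each post-dose timepoint, the "mean placebo-corrected change from baseline with its 90% CI". A separate sentence adds: "Time profile plots of mean difference versus placebo in change from baseline will be presented by dose level for heart rate and QTcF".

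SAP 7.1 removes both with this statement: "Placebo-corrected change from baseline is erroneously mentioned in the protocol but it is not applicable for this study design". The change is listed among those made before unblinding. SAP 3.4.3 keeps the within-treatment summaries: "Actual values (with their 95% CI) and changes from baseline (with their 90% CI) will be tabulated". SAP 6.4.1 defines these as t intervals on the mean of a single group.

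On the design, SAP 1.4 states: "Subjects will be randomised in a 3:1 ratio within each cohort to receive either CHF10067 or placebo". SAP 3.4.1 gives one ECG schedule without distinction by treatment: "ECGs will be performed at Screening visit, at pre-dose on Day 1, and Days 2, 7, 28, and 84 days post-dose". SAP 6.4.2 sets up one placebo column: "All placebo subjects (from all cohorts) will be pooled into one" group. Protocol 1.2 says that placebo serves as the comparator for judging whether an observed effect comes from the treatment or from the conditions of the study.

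**The concern.** The protocol specifies the contrast twice, once as a statistic and once as a plot, which does not look like a slip. The ground given for removing it conflicts with how both documents describe the trial. By comparison, the lung-function deletion in the same SAP section gives a data reason (no normal ranges available); the ECG deletion does not explain why the design rules the contrast out.

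Safety and tolerability are the primary objective. Without this contrast, no planned display gives an interval for any difference between drug and placebo. A one-group interval describes the change in that group. If it is read as a statement about the drug, it understates the uncertainty, because it leaves out the sampling error of the placebo mean.

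**Working it through.** **1. Is it the only such contrast?** In Protocol 12.3, adverse events, laboratory data, vital signs, oxygen saturation, spirometry, diffusing capacity and TG2 are all summarised within dose level or treatment. The pharmacokinetic power model uses dose only. The ECG section alone asks for a difference from placebo.

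**2. Does the design rule it out?** A difference of two group means needs randomised groups, a common baseline and common visits.
- Groups: 3 cohorts × (6 active + 2 placebo) = 24 subjects, that is 18 active and 6 placebo (Protocol 12.1).
- Baseline: a pre-dose ECG on Day 1 for every subject (Protocol 7.2.9, SAP 3.4.1).
- Visits: Days 2, 7, 28 and 84 for every subject (same sections).

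All three are present. The protocol asks for a mean difference, so no subject-level correction is needed. SAP 7.1 itself says, in its note on dose levels, that every analysis separates active from placebo subjects.

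**3. What precision would it have?** The documents give no SD for ECG changes and no power calculation, so there is no planned figure to reproduce. I assume an SD of QTcF change of 10 ms (range 8 to 15), equal in all groups, with planned numbers.

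One group: half-width = t(0.95, n − 1) × SD × √(1/n).
Difference: half-width = t(0.95, n₁ + n₂ − 2) × SD × √(1/n₁ + 1/n₂).

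| 90% interval | n | df | t × root term | Half-width | SD 8 ms | SD 10 ms | SD 15 ms |
|---|---|---|---|---|---|---|---|
| One dose alone (SAP 6.4.1) | 6 | 5 | 2.015 × 0.408 | 0.823 SD | 6.6 | 8.2 | 12.3 |
| One dose minus pooled placebo | 6 v 6 | 10 | 1.812 × 0.577 | 1.046 SD | 8.4 | 10.5 | 15.7 |
| CHF10067 Total alone | 18 | 17 | 1.740 × 0.236 | 0.410 SD | 3.3 | 4.1 | 6.2 |
| CHF10067 Total minus pooled placebo | 18 v 6 | 22 | 1.717 × 0.471 | 0.809 SD | 6.5 | 8.1 | 12.1 |
| One dose minus own-cohort placebo | 6 v 2 | 6 | 1.943 × 0.816 | 1.587 SD | 12.7 | 15.9 | 23.8 |

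Ratios, which do not depend on the SD: 1.046 / 0.823 = 1.27 for one dose, and 0.809 / 0.410 = 1.97 for the Total column. If the SD is instead estimated from all four treatment groups (20 df), the dose-minus-placebo half-width is 1.725 × 0.577 = 0.996 SD, and 0.996 / 0.823 = 1.21.

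Even the least favourable reading, the two placebo subjects of the same cohort, gives an estimate with an interval. The limit is precision, not applicability.

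**The case against.** The best case for the SAP is that little is lost. The study tests no hypothesis, the contrast carries no margin or decision rule, and the dose-escalation rules in Protocol 6.2.2.1 rest on adverse events. The change is disclosed before unblinding. Active and placebo ECG changes remain in one table with n, mean, SD and 90% CI, and on one plot for heart rate and QTcF, so a reader can subtract the means and work out an interval by hand. Every other safety variable is handled side by side in the same way. The protocol names no comparator, and SAP 7.1 notes that dose level could mean cohort, which would leave two placebo subjects. The first scheduled post-dose ECG is on Day 2, while SAP 6.1.3.1 expects the maximum concentration within 1 hour of the end of infusion. Restoring the contrast for three doses gives 4 parameters × 4 visits × 3 doses = 48 intervals at 90%, of which about 4.8 would exclude zero with no drug effect at all.

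Much of this stands as a limit on weight. The interval ratios compare two different quantities, and the SAP does not present the one-group interval as a drug effect. A small and partly non-concurrent placebo group could be a fair reason for caution, and a descriptive label is needed because of the multiplicity. None of it supports the reason the SAP gives. The missing ECG near the peak limits the retained one-group summaries equally.

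**Conclusion.** The concern holds and should be fixed. A planned descriptive display under the primary objective was removed for a reason that the SAP's own account of the randomisation, ECG schedule and pooled placebo group contradicts. The fault is the wrong reason and the lost display; nothing was concealed, and the trial's validity is not in question.

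At planned numbers and equal variances, the omitted interval is 27% wider than the retained one for a single dose (21% with a four-group SD) and 1.97 times as wide for the Total column. The millisecond figures rest on the assumed SD of 8 to 15 ms.

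**What to change.** In SAP 7.1, delete the statement that the contrast does not apply. In SAP 3.4.3 and the display lists, add for heart rate, PR, QRS and QTcF at Days 2, 7, 28 and 84 the mean change for each dose minus pooled placebo, with its 90% CI, and the difference plots for heart rate and QTcF. Label them descriptive, with no adjustment for multiplicity. State that pooled placebo is the chosen comparator because the protocol names none. Add a footnote that, for any dose, four of the six planned placebo subjects come from other, sequential cohorts. CHF10067 Total minus placebo is an optional addition, balanced over cohorts if the planned 6:2 split holds in each.

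If the sponsor still prefers to omit the contrast, SAP 7.1 should give the actual reason, for example a small and partly non-concurrent placebo group.

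The cost is SAP wording, one table and two figures from data already planned. The intervals will be wide and will say nothing about effects at peak concentration.

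A separate, minor point: SAP 7.1 also treats the healthy-subject TG2 summary as a protocol error, although Protocol 7.2.3 plans 24 healthy-subject samples for that comparison. Those two sections need reconciling.
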